12.3. Vital Signs

Systolic blood pressure (mmHg), diastolic blood pressure (mmHg), heart rate (bpm), respiratory rate (breaths per minute), pulse oximetry (%) and temperature (degree Celsius) will be measured at different timepoints as per the SoA in Protocol Section 1.3.

Actual values and changes from baseline in vital sign measurements will be summarized by treatment.

All vital signs will be provided in data listings.

12.4. ECG

The ECG parameters include heart rate, PR, RR, QRS, QT, and corrected QTcF intervals.

12-lead ECGs in triplicate will be taken at at different timepoints as per the SoA in Protocol Section 1.3. 12-lead ECGs should be measured after a minimum of 5 minutes in supine position. The average of the triplicate ECG readings at the time points collected will be calculated and used in the analyses.

An outlier analysis will be performed that will summarize the absolute count, frequency and percentage of participants who meet any of the following outlier criteria at each visit by treatment:

- QT, QTcF interval > 450 msec
- QT, QTcF interval > 480 msec
- QT, QTcF interval > 500 msec
- QT, QTcF interval increases from baseline > 30 msec
- QT, QTcF interval increases from baseline > 60 msec

Actual values and change from baseline of these average ECGs will be summarized by treatment.

All ECG parameters, including all single ECG measurements, but also the mean value and overall ECG evaluation will be provided in data listings.

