#### 5.1. Inclusion Criteria

Male and female participants are eligible to be included in the study only if all of the following criteria apply:

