#### **Medical Conditions**

- 1. History or presence of cardiovascular, respiratory, hepatic, renal, gastrointestinal, endocrinological, hematological, or neurological disorders capable of significantly altering the absorption, metabolism, or elimination of drugs; constituting a risk when taking the study drug; or interfering with the interpretation of data.
- 2. Abnormal blood pressure (BP) as determined by the Investigator (resting BP should be between 140/80 mmHg and 90/60 mmHg) at Screening.
- 3. Participants who have any clinically significant history of allergy or hypersensitivity.
- 4. History of unexplained, recurrent infection, or infection requiring treatment with systemic antibiotics within 90 days prior to dosing on Day 1.
- 5. Participants with a history of frequent and/or chronic headaches, including migraine disorder, cluster headache disorder, and tension headache disorder.
- 6. Previous history of cancer, except for adequately treated basal cell or squamous cell carcinoma of the skin.
- 7. Clinically significant abnormalities and laboratory test results.
- 8. Current or chronic history of liver disease or known hepatic or biliary abnormalities (with the exception of Gilbert's syndrome or asymptomatic gallstones).
- 9. Corrected QT (QTc) > 450 msec for male participants or > 470 msec for female participants.
  - NOTE: The QTc is the QT interval corrected for heart rate according to Fridericia's formula (QTcF). It is either machine-read or manually over-read.
- 10. Female participants who are pregnant or breastfeeding.

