7.2. Key Definitions

End of Study (EOS)

The EOS for each participant is defined as the date the last participant completes the last visit as shown in the Schedule of Activities in Section 1.3 of the Protocol.

Trial day

If the event date \geq date of first dose of IP, trial day = event date – date of first dose of IP + 1. If the event date < date of first dose of IP, trial day = event date – date of first dose of IP.

Nominal Time

Nominal time is the scheduled measurement time relative to time 0. Time 0 is the time of start of study drug dosing on Day 1.

Baseline Value

Baseline value will be defined as the last non-missing value recorded prior to first intake of study treatment.

Change from Baseline (CFB)

Sponsor: Alexion Pharmaceuticals, Inc.; Protocol No.: ALXN1830-HV-108

CFB = Post-baseline value - Value at baseline

7.3. **Missing Data**

For participants who are withdrawn from the study prior to the end of the study, all data collected up to the point of discontinuation will be used for analysis. There will be no imputation for missing data, unless otherwise specified.

7.4. **Visit Windows**

If there are multiple planned assessments for any study procedure at a given time point the latest nonmissing value will be used for summarization. Unscheduled assessments will be listed and will be used to flag baseline visit if this is the last non-missing assessment before the first dose of study drug, but unscheduled assessments will not be included in the summarization.

Pooling of Centers 7.5.

Not Applicable.

7.6. **Subgroups**

Not Applicable.

8. Participant Disposition, Demographic, Other Baseline Characteristics and Medication

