Laboratory parameter values will be graded according to the National Cancer Institute Common Terminology Criteria for Adverse Events (CTCAE).

All summaries will be based on results in SI (standard international system of units) units and will be

output in the order listed above.

Toxicity grading following the NCI CTCAE grades version 5.0 will also be derived for laboratory variables where applicable (see list below). Note, where gradings require investigator/clinical input, this will not be considered and only the numeric criteria will be used for the assignments. If this results in the criteria for more than one grade being met, the highest (worst) CTCAE grade will be assigned. For creatinine only, the criteria based on the upper limit of normal (ULN) will be used (changes compared to the baseline value will not be used), eg, CTCAE defines Grade 1 as > ULN - 1.5 x ULN or > 1 - 1.5 x baseline. Only the ULN – 1.5 x ULN criterion will be used (and not the baseline criterion).

The following parameters are CTCAE gradable:

- Clincal Chemistry: Alanine aminotransferase albumin, alkaline phosphatase, aspartate aminotransferase, total bilirubin, creatinine, gamma-glutamyl transferase, glucose (only do the grading the hypoglycemia, no grading for hyperglycemia), creatine kinase.
- **Hematology**: Absolute neutrophil count (neutrophil), total leukocytes (Leukocytes), hemoglobin (only do the grading for anemia, no grading for hemoglobin increased), platelet count, lymphocyte.
- Coagulation:International normalized ratio.

Actual values and changes from baseline in clinical chemistry, hematology and coagulation, will be summarized by treatment.

Shift tables for clinical chemistry, hematology, and coagulation from baseline CTCAE toxicity for each visit and to the maximum grade on treatment for each parameter will be provided. Participants with both a non-missing baseline and at least one non-missing post-baseline grade will be included in the shift tables. Unscheduled data will be included in the worst case across all scheduled and unscheduled visits after the first dose of study treatment. This means that if there are CTCAE grades derived from both unscheduled and scheduled visits data per test per participant then the highest grade will be summarized.

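### The QT outlier table omits unscheduled ECGs, unlike the laboratory worst-case tables, and neither marks which exceedances are new nor says that QTcF stands apart from QT

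*SAP*

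**What the plan says.** SAP 12.4 averages the triplicate ECGs and then plans an outlier analysis that will "summarize the absolute count, frequency and percentage of participants who meet any of the following outlier criteria at each visit by treatment". There are five criteria. Three are absolute (above 450, 480 and 500 msec) and two are increases from baseline (above 30 and 60 msec). Each is written for both measures, for example "QT, QTcF interval > 450 msec". No limit differs by sex, no exceedance has to be new since baseline, and there is no worst post-baseline row. Protocol 9.4.1 gives the same five criteria, by cohort.

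For unscheduled data the general rule is in SAP 7.4. Such assessments are listed and may serve as baseline, but "unscheduled assessments will not be included in the summarization". SAP 12.2 departs from this for laboratory shift tables: "Unscheduled data will be included in the worst case across all scheduled and unscheduled visits after the first dose of study treatment". It takes the same approach for tests that cannot be graded. SAP 12.4 has no matching sentence.

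On eligibility, Protocol 5.1 admits both sexes, and exclusion criterion 9 in Protocol 5.2 bars "Corrected QT (QTc) > 450 msec for male participants or > 470 msec for female participants". QTc there means the Fridericia-corrected value.

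**The concern.** ECG results are part of the primary safety endpoint, and the safety analysis is descriptive. The counts and percentages in this table are therefore what a reader will take away about QT. Two features make them harder to trust.

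First, the table is closed to unscheduled ECGs. A marked prolongation on such a tracing would leave every row at zero for that participant. The same plan handles an unscheduled laboratory value the opposite way and gives no reason for the difference.

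Second, some entries may say little about the drug. A woman may enter with a QTcF that already exceeds the first cut-off. An uncorrected QT can cross a cut-off because the heart slowed. With 6 active participants planned per cohort, one entry is 1/6 = 16.7% of a full active column.

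**Working it through.** The plan states no figure for this table, so there is nothing to reproduce. The check compares the rules and then applies Fridericia's formula.

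**1. Treatment of unscheduled values**

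| Data | Rule | Unscheduled value in the summary? |
|---|---|---|
| Laboratory, CTCAE-graded (SAP 12.2) | worst case over scheduled and unscheduled visits | yes |
| Laboratory, not gradable (SAP 12.2) | worst case over planned and unscheduled assessments | yes |
| ECG outliers (SAP 12.4 with 7.4) | by visit, no worst-case row | no |

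Under these rules an unscheduled ECG adds 0 to the outlier table, whatever its value.

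**2. Where scheduled ECGs leave a gap** (Protocol 1.3, Tables 4 to 8, 10 and 11)

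- Cohort 3 has 12 dosing days: 1, 8, 15, 22, 29, 36, 43, 50, 57, 64, 71 and 78. Post-dose ECGs are scheduled on Days 1, 8, 22 and 78. The other 8 (Days 15, 29, 36, 43, 50, 57, 64 and 71) have a pre-dose ECG only, and the next scheduled ECG comes 7 days later, before the next dose.
- Cohorts 4 and 5 have 4 dosing days: 1, 8, 15 and 22. Days 8 and 15 are pre-dose only, so 2 of 4.

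Any ECG recorded in the week after one of those doses is unscheduled by definition.

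**3. The QTcF > 450 row**

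Exclusion 9 leaves a band of 451 to 470 msec in which a woman is eligible yet above the first cut-off. A woman stable at 460 in Cohort 1 would be counted at every post-dose ECG time. These are end of infusion, 2, 4 and 12 h (4), Days 2 to 8 (7), and Days 15, 29, 43 and 64 (4), so 4 + 7 + 4 = 15.

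How often this occurs cannot be derived, because the documents give neither the sex mix nor a QTcF distribution. As an illustration, assume that QTcF in women is normal with mean 405 to 425 and SD 15 to 20 msec, truncated at 470. Then 0.13% to 9.46% of eligible women start above 450 (2.48% at mean 415, SD 18). Assume also that half the participants are women, so the share p of all participants is half of that. The chance of at least one in six is 1 − (1 − p)^6:

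- low: p = 0.00065, giving 0.4%
- middle: p = 0.0124, giving 7%
- high: p = 0.0473, giving 25%

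**4. The uncorrected QT rows**

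Fridericia: QTcF = QT / (60/HR)^(1/3), so QT = QTcF × (60/HR)^(1/3). The heart rates below are assumed; the eligibility criteria set no heart-rate limit.

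- QT 450 at 50 bpm: 450 / 1.2^(1/3) = QTcF 423.5. At 45 bpm: 450 / 1.333^(1/3) = QTcF 408.9.
- QTcF fixed at 420, heart rate falling from 70 to 55 bpm: QT goes from 399.0 to 432.4, a rise of 33.4 msec, which meets the > 30 criterion with no change in QTcF.
- The opposite direction: QTcF 505 at 80 bpm is QT 505 × 0.75^(1/3) = 458.8, which meets only the lowest of the three absolute QT criteria.

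**The case against.** The case against is substantial, and much of it stands.

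- **Nothing is lost from the record.** Every single ECG and the overall evaluation are listed, unscheduled ones included. Protocol 10.3.1 puts abnormal ECG results among events that meet the adverse event definition, so a prolongation reported that way would also reach the adverse event tables. The gap is in the outlier table only.
- **Baseline is not ignored.** The > 30 and > 60 msec rows are changes from baseline, and a woman stable at 460 appears in neither. Her entry in the > 450 row is a correct count, because that row is not labelled treatment-emergent. SAP 12.4 also summarizes actual values and changes. If pre-dose visits are tabulated, her value shows there too.
- **The QT problem depends on layout.** With separate rows for QT and QTcF, the QTcF rows are clean. The SAP does not say whether the two are pooled.
- **Little else hangs on it.** There is no inferential safety analysis, and no stopping rule in Protocol 7.2 uses a QT threshold.

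A reader might infer that the table will overcount false outliers and miss true ones. The documents do not support that: they give no data from which an overcount follows, and they keep every tracing visible. Nor do they say that unscheduled ECGs are mostly taken out of concern. The only repeat rule, in Protocol 8.2.3, concerns tracing quality.

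A further tempting step is to count new exceedances only. That would hide real change. A rise from 455 to 479 msec (+24) is not new above 450, not above 480, and not an increase above 30, so only the existing > 450 row shows it.

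**Conclusion.** The point holds as a modest weakness in how the outlier table is built. It is not a contradiction, since SAP and protocol list the same criteria.

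The firm part needs no assumption: under SAP 7.4 and 12.4 a prolongation seen only on an unscheduled ECG is listed but not counted, while SAP 12.2 counts the laboratory equivalent. It has practical weight because 8 of 12 dosing days in Cohort 3 and 2 of 4 in Cohorts 4 and 5 have no scheduled post-dose ECG. How many unscheduled ECGs exist is not known from the documents.

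The other two parts are possibilities, not measured biases. The baseline effect is confined to the > 450 row and to women at 451 to 470 msec; the QTcF > 480, > 500 and change rows are free of it. One such woman is 16.7% of an active column of 6; Cohort 2, with only 2 participants in all, has a smaller denominator. The heart-rate effect is confined to the QT rows, and touches the QTcF result only if the two measures are pooled. The ranges in the working rest wholly on assumed distributions, sex mix and heart rates.

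**What to change.** Change SAP 12.4 as follows.

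1. Add a worst post-baseline row for each criterion, taken over scheduled and unscheduled ECGs after the first dose, as SAP 12.2 does for laboratory values. State how an unscheduled ECG that is not a triplicate enters, and that tracings rejected for quality do not.
2. Report QTcF in its own rows, never pooled with QT, and name it as the outlier measure of interest.
3. Keep the absolute QTcF rows. Beside each, add the number that are new since baseline, meaning baseline at or below that cut-off.
4. Record the change in SAP Section 14, because Protocol 9.4.1 lists the same criteria.

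The cost is one slightly larger table and one line in Section 14; no new data are needed. A worst-case row takes a maximum over many readings, and the number of readings differs between cohorts. Its percentages will tend to exceed the by-visit ones and should be read beside the placebo column.

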12.5. Physical Examination

A full physical examination will be performed at different timepoints as per the SoA (Section 1.3) in the Protocol. A symptom-driven physical examination of relevant body systems may be performed at other times, at the Investigator's discretion.

Physical examination data will be listed.

Interim Analyses

No interim analyses are planned.

13.

Controlled Document ID: **3903A.02**, Effective Date 31-Aug-2020 Filing requirements: TMF

14. Changes from Analysis Planned in Protocol

The study was terminated early, therefore cohort 2 has only 2 participants and cohort 6 has none. Therefore the secondary objective, to compare safety and tolerability, PK, PD, and immunogenicity of ALXN1830 SC between Japanese and non-Japanese healthy participants cannot be met and the secondary endpoint the quantitative assessment of safety, PK parameters, PD parameters, and immunogenicity between Japanese and non-Japanese healthy participants cannot be analyzed.

Analysis sets definitions as specified in Protocol Section 9.3 were updated as follows:

For the Enrolled Set participants also need to be randomized.

For the Pharmacokinetic Set participants need to receive at least 1 dose of study drug (only active) and have at least one post-dose serum ALXN1830 concentration measured. Participants will be analyzed according to the study drug they actually received. Serum concentrations will be summarized for all participants in the PKS. The exclusions from summary statistics for serum concentrations and/or PK parameters will be defined based on review of protocol deviations (if any) prior to database lock by PK scientist and study statistician at the discretion of the sponsor.

For the Pharmacodynamic Set participants need to receive at least 1 dose of study drug (active and placebo) and have evaluable serum Immunoglobulin data (IgG, IgG subtypes, Ig subtypes, CIC) or FcRn.

Immunogenicity Set was not define in the protocol, but added to the SAP as follows: The Immunogenicity Set (IGS) will include all participants who have a predose and at least 1 postdose ADA sample collected. Immunogenicity analyses will be performed using the IGS.

15. Reference List

FDA. Guidance for Industry, Clinical/Medical, Guidance for Industry: Immunogenicity assessment for therapeutic protein product. 2014.

